### 2.5 **Pharmacokinetic population**

#### 2.5.1 **Lu-3BP-227 Pharmacokinetic population**

##### 2.5.1.1 **Lu-3BP-227 blood pharmacokinetic population**

The Lu-3BP-227 blood pharmacokinetic population is all subjects with blood dosimetry data and with no major protocol deviations with an impact on Lu-3BP-227 blood PK analysis.

##### 2.5.1.2 **Lu-3BP-227 urine pharmacokinetic population**

The Lu-3BP-227 urine pharmacokinetic population is all subjects with urine dosimetry data and with no major protocol deviations with an impact on Lu-3BP-227 urine PK analysis.

## 2.5.2 **3BP-227 Pharmacokinetic population**

### 2.5.2.1 *3BP-227 plasma pharmacokinetic population*

The 3BP-227 plasma pharmacokinetic population is all subjects with plasma 3BP-227 concentration data and with no major protocol deviations with an impact on 3BP-227 plasma PK analysis.

### 2.5.2.2 *3BP-227 urine pharmacokinetic population*

The 3BP-227 urine pharmacokinetic population is all subjects with urine 3BP-227 concentration data and with no major protocol deviations with an impact on 3BP-227 urine PK analysis.

## 2.6 **Dosimetry population**

The dosimetry population is all subjects with organ dosimetry data and with no major protocol deviations with an impact on dosimetry analysis.

## 2.7 **Primary population**

The primary objective of this study is safety and tolerability, therefore the primary population for analysis is the safety population.

The pharmacodynamics/efficacy analyses will be based on the pharmacodynamic population, except analyses on tumour response which will be based on the primary pharmacodynamic population and overall survival which will be based on the included population.

The Lu-3BP-227 blood pharmacokinetic analyses will be based on the Lu-3BP-227 blood Pharmacokinetic population.

The Lu-3BP-227 urine pharmacokinetic analyses will be based on the Lu-3BP-227 urine Pharmacokinetic population.

The 3BP-227 plasma pharmacokinetic analyses will be based on the 3BP-227 plasma Pharmacokinetic population.

The 3BP-227 urine pharmacokinetic analyses will be based on the 3BP-227 urine Pharmacokinetic population.

The Lu-3BP-227 pharmacokinetic analyses in discernible organs and target lesions will be based on the dosimetry population.

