#### 1.3.2.2 Pharmacodynamic/efficacy assessments

- Tumour assessment according to Response Evaluation Criteria in Solid Tumors (RECIST) criteria v1.1 for target and non-target lesions assessed locally (by ceCT/MRI) at screening, at Day 1 of cycle 1 (removed from protocol V7.0), at EOCT/ED visit, at Day 29 of second and fourth additional cycles (if applicable), at EOAC/ED visit (if applicable) and every 3 months during long-term follow-up;
- Tumour assessment according to PERCIST criteria v1.0 for target and non-target lesions assessed locally at Day 1 of cycle 1, at EOCT/ED visit and at EOAC/ED visit (if applicable);
- Tumour markers in serum assessed at Day 1 of both cycles 1 and 2, at EOCT/ED visit, at Day 1 of each additional cycle (if applicable) and at EOAC/ED visit (if applicable) including Carcinoembryonic antigen (CEA) (all subjects), Cancer Antigen (CA) 19-9 (all subjects except SCCHN), CA72-4 (subjects with GC) (removed from protocol V7.0), Tissue Polypeptide antigen (TPA) (subjects with SCCHN) (removed from protocol V7.0) and serum Lactate Dehydrogenase (LDH) and Bone Specific Alkaline Phosphatase (BSAP) for ES;

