### 2.2 **Included population**

The included population is all screened subjects who are included in the study and received the therapeutic dose.

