### 2.4 **Pharmacodynamic/Efficacy population**

#### 2.4.1 **Pharmacodynamic population**

The pharmacodynamic population is all subjects who received at least one therapeutic dose and with available post-baseline pharmacodynamics/efficacy data.

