### 3.1.2 *Pharmacodynamic/efficacy endpoints*

The pharmacodynamics/efficacy endpoints are:

- Objective Response Rate (ORR): proportion of subjects with a best overall response (BOR) characterised as either a Complete Response (CR) or Partial Response (PR) according to RECIST criteria v1.1 relative to the total number of evaluable patients;
- Disease Control Rate (DCR): proportion of patients with a BOR characterised as Complete Response (CR), Partial Response (PR) or stable disease (SD) according to RECIST criteria v1.1 relative to the total number of evaluable patients;
- Progression-Free Survival (PFS) from first treatment administration until progression, according to RECIST criteria v1.1;
- Overall Survival (OS) from first treatment administration until death, according to RECIST criteria v1.1;
- Metabolic tumour responses according to PERCIST criteria v1.0;
- Changes in tumour markers in serum relevant and specific to the underlying tumour disease.

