### 3.2.18.4 Progression-Free Survival

The PFS according to local review will include investigator assessed PD and deaths. Other data will be censored. PFS will be assessed at the end of the core trial, at the end of the additional cycles and at the end of the long-term follow-up.

Definition of progression date:

The PD date is assigned to the first time at which PD can be declared.

Definition of censoring date:

Censoring dates are defined in subjects with no PD or death before end of period or withdrawal. In these subjects, the censoring date is defined as the last date on which progression status was 'adequately' assessed. This is taken to be the date of the last radiological assessment at which the target lesions were evaluated by local investigator review.

If no PD is documented, patient will be censored at the last available overall tumour assessment before start of the new anticancer therapy.

Definition of PFS time:

The PFS time will be calculated as the time from first treatment administration to either locally assessed PD or death.

$$\text{PFS time} = [(\text{Date of event} - \text{date of first treatment administration}) + 1] / 7 \text{ (weeks)}$$

The distribution of PFS times will be estimated using the Kaplan-Meier (KM) product limit method.

The Kaplan Meier method will provide hazard curves, life tables, median as well as corresponding 95% Confidence Interval (CI). These statistics will be presented for each treatment group.

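### PFS defaults to a population that requires post-baseline efficacy data, so a treated subject who dies before any is collected drops out of PFS although death is a PFS event

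*SAP*

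**What the plan says.** SAP 2.7 assigns endpoints to populations. Its default reads "The pharmacodynamics/efficacy analyses will be based on the pharmacodynamic population, except analyses on tumour response", and its second exception is "overall survival which will be based on the included population". PFS is named in neither exception. SAP 3.1.2 lists it as an endpoint of its own, apart from ORR and DCR, so the default applies.

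The two populations differ by one condition. The pharmacodynamic population (SAP 2.4.1) is "all subjects who received at least one therapeutic dose and with available post-baseline pharmacodynamics/efficacy data". The included population (SAP 2.2) is "all screened subjects who are included in the study and received the therapeutic dose", with no requirement for later data. Protocol 12.1 applies the same post-baseline condition to efficacy evaluations generally. SAP section 5 declares no changes from the protocol.

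On events, SAP 3.2.18.4 states: "The PFS according to local review will include investigator assessed PD and deaths". Appendix 1 agrees: death is uncensored and takes the date of death. SAP 3.1.2 is shorter, "Progression-Free Survival (PFS) from first treatment administration until progression", and does not mention death.

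On timing, SAP 1.3.2.2 has "Tumour markers in serum assessed at Day 1 of both cycles 1 and 2, at EOCT/ED visit", so the first planned post-baseline marker is at Cycle 2 Day 1. For RECIST scans after screening it gives "at Day 1 of cycle 1 (removed from protocol V7.0), at EOCT/ED visit", which leaves EOCT/ED as the first. The post-baseline FDG-PET is also at EOCT/ED. Protocol 4.2.1 separates the two administrations by 4 to 5 weeks, with 4 more weeks allowed for reversible adverse events.

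**The concern.** Entry to the PFS set depends on something that happens after treatment starts and that an early death can prevent. The subjects at risk of exclusion are those with the shortest PFS times. Whether such a death counts can turn on whether one blood sample was drawn first.

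The same death counts in OS, so the two curves start from different subjects without any stated reason. PFS is presented for each treatment group (SAP 3.2.18.4) and cohorts hold three to five subjects (SAP 1.2), so one omitted event is a large share of a group. Outside Cohort 1, Protocol 4.7.1.3 also allows a subject who stops before the end of Cycle 2 for a reason other than a DLT to be replaced. The cohort can then be refilled while the early event leaves the PFS analysis.

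**Working it through.** The plan gives no PFS target, event count or power, so there is no figure to reproduce. The check has four steps.

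**1. Who is lost.** Take a subject who receives the first therapeutic dose and dies before Cycle 2 Day 1, with no ED visit and no unscheduled scan or marker.
- Included population (2.2): in, because dosed.
- Pharmacodynamic population (2.4.1): out, because there are no post-baseline efficacy data.
- PFS event (3.2.18.4, Appendix 1): yes, on the date of death.
- OS (2.7): counted.

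No other SAP passage returns this subject to PFS. The window is 4 to 5 weeks, or up to 5 + 4 = 9 weeks with a delay.

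**2. Direction and factor.** Let n subjects be treated and k be lost through early death. With no censoring before the last of those deaths, dropping them changes the Kaplan-Meier denominator from n to n - k and leaves every later factor unchanged. After those deaths:

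reported S(t) = S(t) in all treated × n/(n - k).

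The factor exceeds 1 whenever k ≥ 1. Living subjects without post-baseline data do not offset it: censored at Day 1, they leave the risk set before the first event and do not move the curve.

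**3. Size.** The counts k and the underlying PFS values are assumptions.

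| n | k | factor | PFS, all treated | PFS as reported |
|---|---|---|---|---|
| 5 | 1 | 5/4 = 1.250 | 40% | 50.0% |
| 30 | 1 | 30/29 = 1.034 | 50% | 51.7% |
| 30 | 2 | 30/28 = 1.071 | 50% | 53.6% |
| 30 | 3 | 30/27 = 1.111 | 50% | 55.6% |

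The documents give no early death rate. Under exponential survival with median m weeks, the chance of death before week 4 is 1 - 0.5^(4/m): 19% for m = 13, 10% for m = 26 and 7% for m = 39, or about 5.8, 3.0 and 2.1 of 30. These are upper illustrations of k. Entry requires an estimated life expectancy above 3 months (Protocol 5.1.1), and some who die early will have had an ED or unscheduled assessment.

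**4. The censoring rule.** Appendix 1 censors a subject without an event at the last tumour assessment. A living subject with a marker but no post-baseline scan has only the screening scan. The SAP formula is PFS = [(date - first dose date) + 1]/7. A scan on Day -1 gives (-1 + 1)/7 = 0 weeks, and one on Day -21 gives (-21 + 1)/7 = -2.9 weeks. Censoring at Day 1 gives (0 + 1)/7 = 0.14 weeks, which is usable.

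**The case against.** **A death date might itself be efficacy data.** PFS and OS are both listed as efficacy endpoints, so one could argue that nobody is lost. But then every treated subject with known survival status would qualify, and the separate exception for OS would do nothing. The exception shows that the author saw a difference. What stands is that the wording should be made explicit.

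**The ED visit closes most of the gap.** This stands. A reader might infer that subjects who merely deteriorate are also dropped. The documents do not support that. A subject who stops early has an ED visit within 14 days (Protocol 4.7.1.2) with the EOCT assessments (6.2.2.1), which include CT/MRI, FDG-PET and tumour markers (Table 8). Extra scans are allowed when progression is suspected (6.2.4, 10.1.2). Deterioration is also not a PFS event by itself. What remains is death before any of these assessments.

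**The SAP follows the protocol.** True: Protocol 12.1 sets the same condition, so the change is a departure that must be recorded. The SAP has already left that condition for OS, and PFS needs the same step.

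**The loss would be visible.** Reasons for exclusion from each population are tabulated (SAP 3.2.3), deaths are listed (3.2.1.1), and OS counts everyone treated. A reader might infer that PFS and OS cannot be read together. That goes too far: the PFS set is a subset of the OS set and the difference can be traced. Tracing it does not correct the curve, though.

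**PFS might be a tumour response analysis.** A reader might infer that PFS belongs on the primary pharmacodynamic population, which needs two doses and the end of Cycle 2 or EOCT, and so excludes almost all early events. SAP 3.1.2 keeps PFS separate from the response endpoints, and 2.4.2 defines that set for tumour response. The scarcity of early progression comes from the scan schedule and would be seen in any set.

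**Conclusion.** The point holds in a limited, conditional form. By default PFS is analysed on a set that leaves out treated subjects who die before any post-baseline marker, scan or ED assessment, although those deaths are PFS events. If such deaths occur, PFS is biased upward by n/(n - k); if none occur, there is no bias.

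With assumed counts, one lost death in a cohort of 5 moves 40% to 50%, and one to three in 30 move 50% to between 51.7% and 55.6%. This assumes no censoring before the lost deaths. A reader might infer a much larger effect, for instance from six such deaths in 30. The documents give no basis for that count: 20% dead by week 4 to 5 would imply an exponential median survival of about 12 to 16 weeks, with none of the six assessed beforehand.

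A reader might also infer that the phase II decision is at risk. Protocol 1.5 and 1.7 frame that choice around ORR, and no passage makes PFS a decision criterion. PFS is a secondary, descriptive phase I endpoint, so no test, error rate or sample size is affected. It should still be corrected, because the rule conditions on early outcome and the remedy is cheap.

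**What to change.** 1. In SAP 2.7, name PFS together with OS as analysed on the included population.
2. In SAP 3.2.18.4, state that a death without a post-baseline scan is an event on the date of death.
3. In Appendix 1, add a PFS row censoring subjects who are alive with no post-baseline tumour assessment at Day 1, and repeat the rule in 3.2.18.4.
4. In SAP section 5, replace the statement that no changes apply with a note that PFS departs from the post-baseline condition in Protocol 12.1. The existing choice for OS can be noted there too.
5. While editing, add death to the PFS definition in SAP 3.1.2 so that it matches 3.2.18.4.

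The cost is a few sentences and one table row. No new data are needed, because dosing and death dates are already used for OS.

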## 3 **STATISTICAL METHODS**

### 3.1 **Statistical analysis strategy**

The statistical analyses will be performed in accordance with ICH E9 guideline [1]. Statistical analyses described in this document will be performed by Biotrial Biometrics, Rennes, France.

#### 3.1.1 **Safety endpoints**

The safety endpoints are:

- Treatment Emergent Adverse Events (TEAEs), including information on seriousness, intensity, drug relationship and DLTs;
- Clinical laboratory evaluations for haematology, biochemistry, urinalysis, hormones and shift tables;
- Clinical safety endpoints: physical examination, vital signs, body weight, BMI, 12-lead ECGs, 24h 3-lead holter ECGs, serum and urine pregnancy tests, ECOG and specific renal safety biomarkers.

### 3.1.2 *Pharmacodynamic/efficacy endpoints*

The pharmacodynamics/efficacy endpoints are:

- Objective Response Rate (ORR): proportion of subjects with a best overall response (BOR) characterised as either a Complete Response (CR) or Partial Response (PR) according to RECIST criteria v1.1 relative to the total number of evaluable patients;
- Disease Control Rate (DCR): proportion of patients with a BOR characterised as Complete Response (CR), Partial Response (PR) or stable disease (SD) according to RECIST criteria v1.1 relative to the total number of evaluable patients;
- Progression-Free Survival (PFS) from first treatment administration until progression, according to RECIST criteria v1.1;
- Overall Survival (OS) from first treatment administration until death, according to RECIST criteria v1.1;
- Metabolic tumour responses according to PERCIST criteria v1.0;
- Changes in tumour markers in serum relevant and specific to the underlying tumour disease.

### 3.1.3 *Pharmacokinetics, biodistribution and dosimetry endpoints*

#### 3.1.3.1 *Biodistribution and pharmacokinetic endpoints for Lu-3BP-227*

The PK parameters will be derived by non-compartmental analysis (NCA) from individual blood concentrations of Lu-3BP-227 (calculated sample activity):

Concentrations will be decay-corrected for sampling time according to the following formula after subtraction of pre-infusion concentration:

$$A_0 = A_t * \exp((\ln(2) / t_{1/2}) * \Delta t) \text{ where } t_{1/2} = 6.647 \text{ days.}$$

With  $A_t$  the radioactivity at the measurement time,  $A_0$  radioactivity at the sampling time and  $\Delta t$  the time between sampling and measurement time in days.

The PK parameters are the following:

- $C_{max}$  (Bq/mL): Maximum observed Lu-3BP-227 concentration ;
- $T_{max}$  (h): Time of maximal observed Lu-3BP-227 concentration ;
- $AUC_{0-48}$  (MBq/mL\*h): Area under the concentration-time curve of Lu-3BP-227 from start of infusion to 48 hours;
- $AUC_{0-t_{last}}$  (MBq/mL\*h): Area under the concentration-time curve of Lu-3BP-227 from start of infusion to time t corresponding to the last quantifiable concentration;
- $AUC_{0-\infty}$  (MBq/mL\*h): Area under the concentration-time curve from start of infusion to calculated as follows:

$$AUC_{0-\infty} = AUC_{0-t_{last}} + C_{last} / \lambda_z,$$

with  $C_{last}$  as the last quantifiable concentration

- $t_{1/2}$  (h): terminal half-life of activity concentrations of Lu-3BP-227;
- CL (L/h): Total clearance calculated as follows:

$$CL = \text{Dose} / AUC_{0-\infty};$$

- $Vd_z$  (L): Volume of distribution calculated as follows:

$$Vd_z = CL / \lambda_z.$$

- MRT (h): Mean residence time

$$\text{MRT} = \text{AUMC}_{0-\infty} / \text{AUC}_{0-\infty};$$

with  $\text{AUMC}_{0-\infty}$ : Area under the first moment curve from zero to infinity

The following PK parameters will be derived by NCA of the individual urine concentrations of  $^{177}\text{Lu}$ -3BP-227:

- $C_i \times V_i$  (Bq) at each time interval with  $C_i$ : concentrations (calculated sample activity) decay-corrected for start of infusion time (using the same formula as for blood) and  $V_i$ : collected volume
- $A_e$  (Bq): Cumulative activity of drug excreted in urine during 48 hours, calculated as follows:

$$A_e = \sum C_i \times V_i$$

- $F_e$  (%): fraction of the administered drug excreted in urine during 48 hours
- $CL_R$  (L/h): Renal clearance calculated as follows:

$$CL_R = A_e / \text{AUC}_{0-48}$$

The following biodistribution parameters will be derived for target lesions and organs of interest (healthy liver, bone marrow, left kidney, right kidney, spleen and pancreas) by NCA from individual activity uptake of  $^{177}\text{Lu}$ -3BP-227:

- $C_{\max}$  (GBq): Maximum observed  $^{177}\text{Lu}$ -3BP-227 activity uptake;
- $T_{\max}$  (h): Time of maximal observed  $^{177}\text{Lu}$ -3BP-227 activity uptake;
- $\text{AUC}_{0-t_{\text{last}}}$  (GBq\*h): [(Area under the concentration-time curve of  $^{177}\text{Lu}$ -3BP-227 from start of infusion to time t corresponding to the last quantifiable activity uptake (%) in %\*h) \* Radioactivity administered in GBq];
- $\text{AUC}_{0-\infty}$  (GBq\*h): [(Area under the concentration-time curve of  $^{177}\text{Lu}$ -3BP-227 from start of infusion to infinity in %\*h) \* Radioactivity administered in GBq];

$$\text{AUC}_{0-\infty} = \text{AUC}_{0-t_{\text{last}}} + C_{\text{last}}/\lambda_z,$$

with  $C_{\text{last}}$  as the last quantifiable concentration

- MRT (h): Mean residence time

$$\text{MRT} = \text{AUMC}_{0-\infty} / \text{AUC}_{0-\infty};$$

with  $\text{AUMC}_{0-\infty}$ : Area under the first moment curve from zero to infinity

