#### 1.3.2.3 Pharmacokinetics, biodistribution and dosimetry

- Blood samples for pharmacokinetic evaluation of  $^{177}\text{Lu}$ -3BP-227 are collected just before the  $^{177}\text{Lu}$ -3BP-227 infusion (baseline), at the end of infusion (0), 5 minutes  $\pm$ 1 minute, 30 minutes  $\pm$ 5 minutes, 1 hour  $\pm$ 5 minutes (replaced by 90 minutes  $\pm$ 15 minutes from protocol V7.0), 4 hours  $\pm$ 30 minutes, 24 hours  $\pm$ 2 hours, 48 hours  $\pm$ 2 hours, 72 to 96 hours post infusion for both cycles 1 and 2 and for both first and third additional cycles (if applicable) and at 24 hours after the second and fourth additional cycles (if applicable);
- Urine collection for evaluation of the renal excretion of  $^{177}\text{Lu}$ -3BP-227 are collected during four different periods at cycle 1: from 0 (i.e. start of infusion) to 6 hours, 6 to 12 hours, 12 to 24 hours and 24 to 48 hours after the end of infusion (from the start of the IMP infusion to 6 hours after the end of the infusion only for US sites);

- Blood samples for pharmacokinetic evaluation of 3BP-227 are collected at cycle 1 only before the infusion (baseline), at the end of infusion of  $^{177}\text{Lu}$ -3BP-227 (0), 5 minutes  $\pm$  1 minute, 30 minutes  $\pm$  5 minutes, 1 hour  $\pm$  5 minutes (replaced by 90 minutes  $\pm$  15 minutes from protocol V7.0), 4 hours  $\pm$  30 minutes, 6 hours  $\pm$  30 minutes, 10 hours  $\pm$  1 hour (replaced by 8 hours  $\pm$  1 hour from protocol V7.0), 24 hours  $\pm$  2 hours and 48 hours  $\pm$  2 hours after the end of infusion of  $^{177}\text{Lu}$ -3BP-227;
- Urine collection for evaluation of the renal excretion of 3BP-227 are collected during four different periods at cycle 1: from 0 (i.e. start of infusion) to 6 hours, 6 to 12 hours, 12 to 24 hours and 24 to 48 hours after the start of infusion (from the start of the IMP infusion to 6 hours after the end of the infusion only for US sites);

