### 3.1.3.2 Pharmacokinetic endpoints for 3BP-227

The following PK parameters will be derived by NCA of the plasma concentration-time profiles during cycle 1:

- $C_{\max}$  (ng/mL): Maximum observed 3BP-227 plasma drug concentration;
- $\text{AUC}_{0-t_{\text{last}}}$  (ng/mL\*h): Area under the plasma concentration-time curve of 3BP-227 from start of infusion to time t corresponding to the last quantifiable concentration
- $\text{AUC}_{0-\infty}$  (ng/mL\*h): Area under the plasma concentration-time curve of 3BP-227 from start of infusion to infinity calculated as follows:

$$\text{AUC}_{0-\infty} = \text{AUC}_{0-t_{\text{last}}} + C_{\text{last}}/\lambda_z,$$

with  $C_{\text{last}}$  as the last quantifiable concentration

- $t_{1/2}$  (h): Terminal elimination half-life calculated as follows:

$$t_{1/2} = \text{Ln}(2)/\lambda_z$$

- CL (L/h): Total clearance from plasma calculated as follows:

$$CL = \text{Dose} / AUC_{0-\infty}$$

- $V_z$  (L): Volume of distribution from plasma calculated as follows:

$$Vd_z = CL / \lambda_z$$

- MRT (h): Mean residence time

$$MRT = AUMC_{0-\infty} / AUC_{0-\infty}$$

with  $AUMC_{0-\infty}$ : Area under the first moment curve from zero to infinity

The following PK parameters will be derived by NCA of the individual urine concentrations:

- $C_i \times V_i$  (ng) at each time interval with  $C_i$ : concentrations and  $V_i$ : collected volume
- $A_e$  (ng): Cumulative amount of drug excreted in urine during 48 hours, calculated as follows:

$$A_e = \sum C_i \times V_i$$

- $F_e$  (%): fraction of the administered drug excreted in urine during 48 hours
- $CL_R$  (L/h): Renal clearance calculated as follows:

$$CL_R = A_e / AUC_{0-\text{last}}$$

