### 3.2.19.3 *Analyses on urine pharmacokinetics of Lu-3BP-227*

Urine total activity concentrations (including PK urine sampling dates and times) will be listed, amount of drug excreted in urine will be summarised by time interval and overall and urine PK parameters will be listed and summarised at cycle 1 as described in section 3.2.19.1.1.

Individual cumulative urine recovered activity versus time profiles of Lu-3BP-227 will be presented graphically at cycle 1 for each treatment group with all subjects on the same graph.

The graph of cumulative recovered activity in urine over time will be provided for urine total activity concentration of  $^{177}\text{Lu}$ -3BP-227 at cycle 1 with all treatment groups on the same graph.

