#### 3.2.19.5 *Analyses on urine pharmacokinetics of 3BP-227*

Urine total activity concentrations (including PK urine sampling dates and times) will be listed, cumulative amount of drug excreted in urine will be summarised by time interval and overall and urine PK parameters will be listed and summarised at cycle 1 as described in section 3.2.19.1.1.

Individual urine cumulative recovered amount versus time profiles of 3BP-227 will be presented graphically at cycle 1 for each treatment group with all subjects on the same graph.

The graph of urine cumulative recovered amount ( $A_e$ ) over time will be provided for urine concentration of 3BP-227 at cycle 1 with all treatment groups on the same graph.

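### Ae and Fe are defined over 48 h for every subject, but US urine collection stops 6 h after infusion, and the SAP gives no rule for US Ae, Fe or CL_R

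*SAP*

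**What the plan says.** SAP 3.1.3.1 (177Lu-3BP-227) defines Ae as "Cumulative activity of drug excreted in urine during 48 hours, calculated as follows", the sum of concentration times volume over the intervals. It defines Fe as the "fraction of the administered drug excreted in urine during 48 hours" and sets CL_R = Ae/AUC0-48. SAP 3.1.3.2 (3BP-227) defines Ae as "Cumulative amount of drug excreted in urine during 48 hours, calculated as follows" and sets CL_R = Ae/AUC0-last. Neither section distinguishes sites.

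SAP 1.3.2.3 gives four urine intervals up to 48 h, then restricts collection for both analytes: "from the start of the IMP infusion to 6 hours after the end of the infusion only for US sites". Footnotes m and t of SAP Table 1 and Protocol 9.1.2 and 9.3.2 agree. Blood and plasma sampling has no US exception. The urine PK populations (SAP 2.5.1.2 and 2.5.2.2) do not exclude US subjects, and SAP section 5 lists no changes from the protocol.

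On decay, blood follows this rule: "Concentrations will be decay-corrected for sampling time according to the following formula after subtraction of pre-infusion concentration". The time difference in that formula runs from sampling to measurement. Urine is to be "decay-corrected for start of infusion time (using the same formula as for blood").

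The urine output sections plan by-interval summaries: "amount of drug excreted in urine will be summarised by time interval and overall" for 177Lu (SAP 3.2.19.3) and "cumulative amount of drug excreted in urine will be summarised by time interval and overall" for 3BP-227 (SAP 3.2.19.5).

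**The concern.** A US subject has one urine collection of about 6.33 h (20 min infusion plus 6 h), so the 48 h Ae and Fe cannot be observed. Two programmers following the SAP could do different things. One sums what was collected and labels it 48 h, so that CL_R sets 6.33 h of urine against 48 h of blood. The other sets Ae to missing, which removes US subjects from Ae, Fe and CL_R. The statement in SAP 3.2.2.1 that missing values are not replaced does not settle which.

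Ae and CL_R of 3BP-227 are named secondary endpoints (Protocol 4.4.2.1), and three of about eleven planned escalation centres are in the US (Protocol synopsis). At stake are the overall urine row, Fe and CL_R in cohorts of three to five subjects. They could mix 6 h and 48 h quantities under one label, or lose subjects.

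Separately, the blood decay formula cannot carry a urine value back to the start of infusion, because its time difference begins at sampling. The urine reference time is therefore unclear, and it may differ from the one used for the blood AUC in the same ratio.

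**Working it through.** The plan states no figure to reproduce, so this check compares definitions and then illustrates size.

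**Inputs.** From the documents: infusion 20 min (Protocol 7.1.4.1), so D = 0.333 h and US urine ends at T = 6.333 h from the start; physical half-life 6.647 days = 159.5 h (SAP 3.1.3.1), so λ = ln 2/159.5 = 0.004345 per h. Assumed, because the documents give no human values: one compartment, constant renal clearance, biological half-life h of 1, 2, 2.15 or 5 h, with k = ln 2/h. The 2.15 h value is the dog half-life of unlabelled 3BP-227 (Protocol 1.3.3), the longest animal value given there.

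**Formulas.** Decay-free AUC to time T > D is proportional to A(T) = 1 − e^(−kT) × (e^(kD) − 1)/(kD). U(T) is the same integral with the factor e^(−λt) left in, which is blood corrected only to sampling time. With constant renal clearance, Ae is proportional to A.

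**Example, h = 2 h.** k = 0.3466 and kD = 0.1155, so (e^(kD) − 1)/(kD) = 1.060. e^(−k × 6.333) = 0.1114. A(6.333) = 1 − 0.1114 × 1.060 = 0.882, and A(48.33) is 1.000 to three decimals. U(48) = 0.987. The US Ae ratio is 0.882, and US 177Lu CL_R is 0.882/0.987 = 0.894 of true.

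**Results if the collected interval is summed**

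| Quantity (ratio to true) | 1 h | 2 h | 2.15 h | 5 h |
|---|---|---|---|---|
| US Ae and Fe: A(6.33)/A(48.33) | 0.99 | 0.88 | 0.86 | 0.58 |
| US 177Lu CL_R, urine referenced to start of infusion: A(6.33)/U(48) | 0.99 | 0.89 | 0.88 | 0.59 |
| US 3BP-227 CL_R, last sample 8 h after infusion: A(6.33)/A(8.33) | 0.99 | 0.94 | 0.93 | 0.85 |

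For 3BP-227 there is no bias of this kind if the last quantifiable sample is the 6 h one, because the windows then coincide.

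**Results if US values are set to missing.** SAP 3.2.19.1.1 displays descriptive statistics only when at least 2/3 of the data are available. One US subject in a cohort of 3, 4 or 5 leaves 2/3, 3/4 or 4/5 (67%, 75%, 80%), so statistics are shown. Two leave 1/3, 2/4 or 3/5 (33%, 50%, 60%), so only minimum and maximum appear. US enrolment per cohort is not given.

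**Decay reference.** Over 48 h the decay factor is e^(48λ) = 1.232. If urine is referenced to the start of infusion and blood to sampling, non-US 177Lu CL_R is overstated by A(48)/U(48) = 1.007, 1.013, 1.014 and 1.032 at 1, 2, 2.15 and 5 h, and by 1.079 at 20 h.

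Total CL = Dose/AUC0-∞ uses the same blood basis. If the dose is referenced to the start of infusion, CL_R/CL as written is 1.000 of the true fraction at 1 to 5 h and 0.958 at 20 h. Re-referencing CL_R alone would move it to 0.993, 0.987, 0.986, 0.969 and 0.888 at 1, 2, 2.15, 5 and 20 h.

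**First-interval comparability.** For 177Lu the first interval ends 6 h after infusion at all sites. For 3BP-227 it ends 6 h after the start of infusion outside the US, 20 min earlier than in the US: A(6)/A(6.33) = 0.996, 0.984, 0.982 and 0.965.

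**The case against.** The strongest reply is that nothing need be mixed. A subject without urine from 6 to 48 h does not meet the 48 h definition, so the value is simply unavailable, as a consequence of the collection schedule. A sponsor PK instruction that SAP 3.2.19.1.1 makes binding is redacted, as are SAP appendix pages, and either may hold a rule. By-interval summaries already allow cross-site comparison. Within the animal half-lives in Protocol 1.3.3 (0.26 to 2.15 h), the Ae shortfall is at most about 14%.

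Much of this stands. A reader might infer that US CL_R definitely uses unmatched intervals. The SAP does not say so; that follows only if the collected interval is summed, which the Ae formula suggests but does not settle. A reader might also infer a proven decay error at all sites. The urine wording is ambiguous: applied literally, the blood formula would reference urine to sampling, and the mismatch would largely disappear.

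What remains is that the visible definitions say 48 h for everyone and carry no exception. The by-interval summaries do not repair the overall row, Fe or CL_R. The 14% figure comes from unlabelled compound in animals and does not bound 177Lu activity in human blood.

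**Conclusion.** The SAP lacks a rule for US urine parameters. Summing the collected interval understates US Ae and Fe and biases US 177Lu CL_R low. It biases US 3BP-227 CL_R low only when the last quantifiable sample is later than about 6.3 h from the start of infusion. Treating the values as missing drops US subjects instead.

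The size rests on assumed half-lives and a mono-exponential model: negligible near 1 h, roughly 11 to 14% for Ae and 177Lu CL_R near 2 h, and about 40% at 5 h. No passage supports the longer values. The decay point is a wording gap worth about 1 to 3% in 177Lu CL_R at 1 to 5 h if urine is referenced to the start of infusion, and total CL then carries nearly the same factor.

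A reader might infer an effect on dose decisions. The documents do not support that: the DLT, MTCA and organ-limit rules do not use these parameters. They are descriptive PK outputs, and CL_R of 177Lu is defined only in the SAP. The gap should be closed before the tables are final.

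**What to change.** 1. Define CL_R = Ae(0–T)/AUC(0–T) over each subject's actual urine interval: 48 h, or 6 h after the end of infusion at US sites. For US 3BP-227 use the existing 6 h plasma sample. For US 177Lu, interpolate blood log-linearly between the 4 h and 24 h samples and flag the value as approximate. The interpolation error in AUC is nil for mono-exponential decline and about +2% in biphasic examples (70% of AUC at a 1 h half-life with 30% at 12 h; 90% at 1 h with 10% at 20 h). State how AUC is completed if the last quantifiable sample precedes T, and whether the flag counts against the 2/3 unflagged condition in SAP 3.2.19.1.1.

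2. Report 48 h Ae and Fe, and the overall urine row, only for subjects with 0–48 h urine. Use the by-interval summaries for cross-site comparison, with a footnote on the 20-minute difference in the first 3BP-227 interval.

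3. State the urine time difference explicitly as start of infusion to measurement. If blood is re-referenced to the start of infusion for CL_R, use the same AUC basis for total CL and Vdz. Otherwise leave both on the current basis and footnote the reference times.

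The cost is SAP wording, footnotes and modest programming. No new samples are needed. The drawback is that US 177Lu CL_R rests on an interpolated AUC.
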